8.5 Recording of Adverse Events

i) Time Period for Collection of Adverse Events

All AEs and SAEs will be collected from the signing of the ICF until the follow-up visit and as soon as informed to the investigator.

ii) Follow-up of Unresolved Adverse Events

Any AEs, including SAEs, AEs leading to discontinuation of the study treatment and AESIs that are present at the subject's last assessment as appropriate in the study, will be followed up by the Investigator for as long as medically indicated and the outcome of the AE will be updated in the applicable eCRF, if needed. Sponsor retains the right to request additional information for any subject with ongoing AE/SAE(s) at the end of the study, if judged necessary.

iii) Variables

The following variables will be collected on the applicable report form for each AE:

- AE (verbatim)
- Date when the AE started and stopped or if it is ongoing
- Maximum intensity
- Whether the AE is serious or not
- Investigator causality rating against the study treatment
- Action taken about the study treatment
- Whether the AE led to the subject's withdrawal from the study
- Outcome

In addition, the following variables will be collected on the applicable report form for SAEs:

- Date AE met criteria for SAE
- Date Investigator became aware of SAE
- Reason AE is serious
- Date of hospitalization
- Date of discharge
- Probable cause of death
- Date of death
- Autopsy performed
- Causality assessment in relation to study procedure(s)
- Description of AE

It is important to distinguish between serious and severe AEs. Severity is a measure of intensity whereas seriousness is defined by the criteria in Section 8.4. An AE of severe intensity need not necessarily be considered serious. For example, nausea that persists for several hours may be considered severe nausea, but not an SAE unless it meets the criteria presented in Section 8.4. On the other hand, a stroke that results in only a limited degree of disability may be considered a mild stroke but would be an SAE when it satisfies the criteria.

Intensity rating scale to be used:

- Mild: Mild symptoms causing no or minimal interference with usual social and functional activities, with intervention not indicated.
- Moderate: Moderate symptoms causing greater than minimal interference with usual social and functional activities, with intervention indicated.
- Severe: Severe symptoms causing inability to perform usual social and functional activities, with

intervention or hospitalization indicated.

iv) Causality Collection

The Investigator will assess causal relationship between the study treatment and each AE, SAE, AE leading to discontinuation, and AESIs.

The causal relationship will also be assessed for other medications and study procedures. Note that for AEs that could be associated with any study procedure the causal relationship is implied as “related”.

The Investigator is obligated to assess the relationship between study treatment and each occurrence of each AE/SAE. The AE must be characterized as unrelated, unlikely to be related, possibly related, or probably related.

- “Probably related” conveys that there are facts, evidence, and/or arguments to suggest a causal relationship, rather than a relationship cannot be ruled out.

- “Possibly related” suggests that the association of the AE with the study treatment is unknown; however, the AE is not reasonably supported by other conditions.

- “Unlikely to be related” suggests that only a remote connection exists between the study treatment and the AE. Other conditions, including chronic illness, progression, expression of the disease state, or reaction to concomitant therapy appear to explain the reported AE.

- “Unrelated” is used if there is not a reasonable possibility that the study treatment caused the AE. The Investigator will use clinical judgment to determine the relationship.

- Alternative causes, such as underlying disease(s), concomitant therapy, and other risk factors, as well as the temporal relationship of the event to study treatment administration, will be considered and investigated.

- The Investigator will also consult the Investigator’s Brochure IB and/or Product Information for marketed products in his/her assessment.

- For each AE/SAE, the Investigator must document in the medical notes that he/she has reviewed the AE/SAE and has provided an assessment of causality.

- There may be situations in which an SAE has occurred, and the Investigator has minimal information to include in the initial report. However, it is very important that the Investigator always makes an assessment of causality for every event before the initial transmission of the SAE data.

- The Investigator may change his/her opinion of causality in light of follow-up information and send an SAE follow-up report with the updated causality assessment.

- The causality assessment is one of the criteria used when determining regulatory reporting requirements.

v) Collection of Adverse Events Based on Signs and Symptoms

When entering AEs in the eCRF, the recording of diagnoses is preferred (if known) over recording a list of signs and symptoms. However, if a diagnosis is known and there are other signs or symptoms that are not consistent with the diagnosis, the diagnosis and each sign or symptom will be recorded separately.

vi) Collection of Adverse Events Based on Examinations and Tests

Any clinically significant abnormal laboratory result should be considered as an AE. If a clinically significant abnormal laboratory result meets at least one of the SAE criteria, then it should be reported as an SAE (Section 8.4).

Any clinically significant abnormal vital sign or other finding at a physical examination that meets at least one of the SAE criteria should also be considered and reported as an SAE.

If clinically significant abnormal laboratory results meet AESI criteria, then these results should be considered as AESI (Section 8.3).

vii) Hy's Law

Hy's Law cases represent one end of a spectrum of laboratory abnormalities that indicate liver injury. Cases where a subject has an AST or ALT $\geq 3 \times \text{ULN}$ and total bilirubin $\geq 2 \times \text{ULN}$ and international normalized ratio (INR) > 1.5 , if INR measured, which may indicate severe liver injury may need to be reported as SAEs.

vii) Collection of Adverse Events of Special Interest

Adverse events of special interest will be collected and recorded in the applicable eCRF. Anti-drug antibodies (ADAs) and neutralizing antibodies (Nabs) will be measured at baseline, 12-weeks and 24-weeks of therapy as well as the 4-week post treatment follow up. If any subjects develop ADAs and Nabs, we will monitor them at for an additional 3 months from the last observation to document resolution of the antibodies. Additionally, ADA should be measured in the event of loss of efficacy, worsening metabolic parameters, and any severe and/or serious infection. If ADAs are observed, titers should be reported, and neutralizing activity should be assessed. We will continue to monitor ADAs and AEs until ADAs have cleared this 6-month intervals.

ix) Collection of Pregnancies

If a female subject, or if a female partner of a male subject, becomes pregnant while enrolled in the study, a paper Pregnancy Report Form should be completed and submitted to the Sponsor designee within 24 hours of the treating physician's/research personnel's awareness of the pregnancy. Every effort should be made to follow the pregnancy until completion or until pregnancy termination.

If the outcome of the pregnancy meets the criteria for immediate classification as an SAE (i.e., spontaneous abortion, stillbirth, neonatal death, or congenital anomaly [including that in an aborted fetus, stillbirth, or neonatal death]), the Investigator should follow the procedures for reporting SAEs.

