Arthralgia	4 (8)
Dizziness	4 (8)
Ear infection	4 (8)
Fatigue	4 (8)
Nausea	4 (8)
Ovarian cyst	4 (8)
Upper respiratory tract infection	4 (8)
Anemia	3 (6)
Back pain	3 (6)
Diarrhea	3 (6)
Paresthesia	3 (6)
Proteinuria	3 (6)
Pyrexia	3 (6)

Frequent AEs that were considered by the investigator to be related to metreleptin treatment included hypoglycemia, fatigue, nausea, and decreased weight, although there was no difference in incidence of fatigue or nausea between metreleptin-treated and placebo-treated obese subjects (without lipodystrophy) in the integrated Amgen obesity safety studies.

In the pivotal study, 11% of patients reported hypoglycemia. The majority of hypoglycemia events were mild or moderate, and most occurred in the setting of insulin use (alone or with oral agents). In the integrated Amgen obesity studies, hypoglycemia was more frequent in metreleptin-treated versus placebo-treated subjects (3.6% vs. 1.4%). The most notable safety observation in the generalized LD patient population was the observation of 2 cases of peripheral T-cell lymphoma not otherwise specified (PTCLNOS) and 1 case of ALK+ anaplastic large cell lymphoma (ALCL) in the NIH studies. All 3 events occurred in patients with a specific type of LD (acquired generalized lipodystrophy) and the 2 events of PTCL-NOS occurred in patients who had significant hematologic

abnormalities. The ALK+ ALCL occurred in the setting of a chromosomal translocation, and metreleptin had no evidence of mutagenicity in toxicology studies. Thus, based on the available evidence, the development of peripheral T-cell lymphoma is likely associated with the underlying acquired LD disease but a potential contribution of metreleptin to progression cannot be entirely excluded.

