Patients with LD are predisposed to acute pancreatitis due to severe and sometimes extreme hypertriglyceridemia. During metreleptin treatment, 7% of patients had an episode of pancreatitis. All had a history of pancreatitis and most had a history of hypertriglyceridemia. Four patients had abrupt withdrawal or suspected non-compliance with metreleptin. Thus, despite metreleptin effects to substantially reduce TG, some patients likely remain predisposed to developing pancreatitis due to prior history of pancreatitis and/or continuing hypertriglyceridemia (e.g., if they are not compliant with or discontinue metreleptin therapy). (In the NIH and FHA101 studies, 4 patients experienced events of hypersensitivity (1 with anaphylaxis attributed to food, and 3 with events of urticaria). All patients continued metreleptin treatment without further events, suggesting that the events were not related to metreleptin. However, in the integrated Amgen obesity studies, events of hypersensitivity occurred more commonly with metreleptin versus placebo treatment (3.3% vs. 1.4%) although the incidence was low.

Neutralizing activity has been observed in patients treated with metreleptin in clinical studies (obesity and lipodystrophy development programs). The development of neutralizing activity could neutralize the activity of metreleptin, resulting in loss of efficacy, as well as neutralize the activity of endogenous leptin, potentially affecting normal physiological processes regulated by leptin (including immune function). In lipodystrophy patients who are leptin deficient at baseline, the consequences of neutralizing endogenous leptin are not clear. There was evidence of loss of efficacy in the lipodystrophy patients who developed neutralizing activity to metreleptin. Sepsis was reported in 2 LD patients who also had other factors that could predispose them to infection but has not been consistently associated with neutralizing activity.

Leptin has a known role in regulating immune function that is complex. This has relevance given the potentially dysregulated immune systems of LD patients (especially those with acquired LD and/or autoimmunity). How mitofusin 2 affects immune function is not known.

In this study, we will treat four patients from our cohort with Mitofusin 2 defects. We can broaden the studies if we have a positive signal in these cases.

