8.6 Reporting of Serious Adverse Events

All SAEs must be reported whether or not considered causally related to the study treatment, or to the study procedures (Section 8.4). All SAEs will be recorded in the applicable eCRF.

If an SAE occurs during the course of the study, then Investigators or other site personnel must inform the Sponsor designee per Section 8.8 immediately but no later than 24 hours of the Investigator's awareness of the event.

The investigator must report all events meeting the criteria and definition of a serious adverse event as per the local IRB reporting requirements.

If an IND is required for this study, the investigator will coordinate with the Michigan Institute for Clinical and Health Research (MICHR) IND/IDE Assistance Program (MIAP) office for reporting of any and all IND safety reports to the FDA as per the requirements outlined in 21 CFR312.32. This includes reporting of all Serious Adverse Events (SAEs) that are both unexpected and related to the drug as soon as possible, but in no case later than 15 calendar days after the sponsor determines that the information qualifies for reporting. If the unexpected and related SAE is either fatal or life-threatening, then the SAE must be reported as soon as possible but in no case later than 7 calendar days after the sponsor's initial receipt of the information. A summary of all non-expedited safety reports will be submitted in the annual report.

For fatal or life-threatening SAEs where important or relevant information is missing, active follow-up is undertaken immediately. Investigators or other site personnel will inform the Sponsor designee of any follow-up information on a previously reported SAE immediately but no later than 24 hours of the Investigator's awareness of the event.

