8.9 Management of the Study Treatment-related Toxicities

There have been reports of generalized hypersensitivity (e.g., urticaria or generalized rash) in subjects taking metreleptin. If a hypersensitivity reaction occurs, the Investigator should discuss the proper clinical treatment for the event, including possible discontinuation of the study treatment with the subject. Dosage adjustments, including possible large reductions of insulin or insulin secretagogue (e.g., sulfonylurea) may be necessary in some subjects to minimize the risk of hypoglycemia.

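### Section 8.5 iv has no causality level for an adverse event with a plausible but unproven drug role and another plausible cause, and its wording tends to draw such events down to *unlikely to be related*

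*Protocol*

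**What the plan says.** Protocol section 8.5 iv (Causality Collection) makes the investigator place each adverse event in one of four levels with respect to study treatment:

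- *Probably related*: there are positive grounds for a causal link, as opposed to a link that simply cannot be excluded.
- *Possibly related*: the association with treatment is unknown, but "the AE is not reasonably supported by other conditions".
- *Unlikely to be related*: this level "suggests that only a remote connection exists between the study treatment and the AE". The definition continues: "Other conditions, including chronic illness, progression, expression of the disease state, or reaction to concomitant therapy appear to explain the reported AE".
- *Unrelated*: there is no reasonable possibility that the drug caused the event.

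The section asks the investigator to use clinical judgment, to weigh alternative causes and timing, and to consult the Investigator's Brochure or product information. It adds that the rating is one of the criteria for regulatory reporting.

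Section 8.6 applies the idea of relatedness if an IND is required: "This includes reporting of all Serious Adverse Events (SAEs) that are both unexpected and related to the drug". Neither section says which of the four levels count as related.

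**The concern.** The definition of *possibly related* makes the absence of another reasonable explanation a condition of the rating. Patients with a rare metabolic disease often have such an explanation. Section 1.4 says of the earlier metreleptin data that comorbidities and the lack of a placebo arm limit any judgement of relatedness. The present study is also uncontrolled, enrols four patients, has safety as a stated objective (section 2.1) and plans result tables without formal testing (section 9.1). The investigator's rating therefore carries much of the weight of attribution.

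If the scale has no place for a contributory drug role, any table of events by relatedness will understate the drug's part. If an IND applies, an unexpected serious event could also be classed as not related because of the wording of the scale and not because of a clinical judgement.

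**Working it through.** There is no arithmetic here. The check sets the four definitions beside one type of event: a drug contribution is plausible but unproven, and a comorbidity or co-medication is also a plausible cause.

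| Level | What it requires | Does this event meet it? |
|---|---|---|
| Probably related | Positive grounds for causation, more than inability to exclude it | No: the role is plausible only |
| Possibly related | Unknown association and no other condition reasonably supporting the event | No: another cause is plausible |
| Unlikely to be related | Only a remote drug connection, with other conditions appearing to explain the event | First part no, second part often yes |
| Unrelated | No reasonable possibility of causation | No: the possibility is reasonable |

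No level fits, yet one must be chosen. *Unlikely* is the nearest, because its second part lists disease expression and concomitant therapy.

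The gap is specific, as varying the event shows:

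1. Another cause is plausible and there is positive evidence of a drug contribution. *Probably related* is open, since that level does not require other causes to be absent.
2. Another cause is plausible and the drug contribution is plausible but unproven. No level fits, and the event tends to go to *unlikely*.
3. Another cause is plausible and the drug connection is remote. *Unlikely* fits properly.
4. No other cause is plausible and the association is unknown. *Possibly related* fits.

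Only case 2 is mishandled. Section 1.4 shows that it is realistic. On the three T-cell lymphomas in earlier studies, the protocol concludes that the underlying acquired lipodystrophy is the likely cause but that a contribution of metreleptin to progression cannot be fully excluded. The disease bars *possibly related*, and the reservation about the drug is the kind of statement that *probably related* rules out. A rater who thinks the contribution remote may use *unlikely*. A rater who thinks it reasonably possible has nowhere to go.

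The same section supplies a mixed picture for pancreatitis: "All had a history of pancreatitis and most had a history of hypertriglyceridemia". Four patients had also stopped metreleptin abruptly or were suspected of not taking it, so background disease and treatment exposure were both in play.

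Section 8.5 iv is also uneven within itself. For study procedures, an event that could be associated with one is taken as related. That is a far lower threshold than the one for the drug, and plain *related* is not one of the four levels.

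**The case against.** The strongest reply is that the scale is applied by a clinician and leaves room. *Probably related* tolerates competing causes, *unlikely* requires a remote connection, and timing and product information must be weighed. This stands for events with positive evidence. It does not close the gap, because judgment must still end in one of the four defined levels, and weighing an alternative cause leads directly to the exclusion in *possibly related*.

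Three stronger readings are tempting, and the protocol does not support them.

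- A reader might infer that hypoglycaemia in patients on insulin must be rated *unlikely* even when the drug contributed. Section 1.4 reports hypoglycaemia in 3.6% on metreleptin against 1.4% on placebo in the obesity studies. Section 8.9 says that reductions of insulin or a secretagogue "may be necessary in some subjects to minimize the risk of hypoglycemia". A rater can use these as grounds for *probably related*. Insulin use in the enrolled patients cannot be checked in the text available.
- A reader might infer from the universal history of pancreatitis that none of the earlier cases (7% of patients) could be *possibly related*. A history does not settle whether each new episode is reasonably explained by it.
- A reader might infer that safety reporting as a whole is compromised. Sections 8.4, 8.6 and 8.8 send serious events and the listed events of special interest to the sponsor within 24 hours whatever the causality.

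The FDA route is also narrow. It applies only if an IND is required, it needs the event to be unexpected, and the investigator's rating is only one input. Hypoglycaemia is already a listed reaction, so the effect on expedited reporting there is probably small. With four patients, timing, action taken and outcome are recorded for each event and can be read individually. These points limit the consequence but leave the definition defective.

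**Conclusion.** The point holds as a gap in the scale. An event with a plausible but unproven drug role and another plausible cause meets none of the four mandatory levels, and the wording favours *unlikely*. The direction is under-attribution to the drug.

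The size cannot be quantified. It depends on how many such events occur in four patients and on how each rater resolves the mismatch, and the protocol gives no figure for either. The affected outputs are any presentation of events by relatedness and, conditional on an IND, FDA reporting of unexpected related serious events. The missing statement of which levels count as related adds to the second.

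The conclusion assumes that the definitions are applied as worded. A rater who ignores the exclusion and uses *possibly related* in its everyday sense would avoid the problem, but would then be departing from the protocol.

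**What to change.** In section 8.5 iv:

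- Redefine *possibly related* as a reasonable possibility that study treatment caused or contributed to the event, even if another condition or co-medication is also a plausible cause.
- Keep *unlikely to be related* for events where the drug connection is remote. The presence of another explanation should not be enough by itself.
- State, with a cross-reference in section 8.6, that *possibly* and *probably related* both count as related.

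This takes two or three sentences and changes nothing in treatment, visits or data collection. The downside is that somewhat more events will be labelled related. Section 3.1 shows that patients are already on treatment, so any events already rated should be reviewed once against the revised wording. With four patients that is a small task.

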8.6 Reporting of Serious Adverse Events

All SAEs must be reported whether or not considered causally related to the study treatment, or to the study procedures (Section 8.4). All SAEs will be recorded in the applicable eCRF.

If an SAE occurs during the course of the study, then Investigators or other site personnel must inform the Sponsor designee per Section 8.8 immediately but no later than 24 hours of the Investigator's awareness of the event.

The investigator must report all events meeting the criteria and definition of a serious adverse event as per the local IRB reporting requirements.

If an IND is required for this study, the investigator will coordinate with the Michigan Institute for Clinical and Health Research (MICHR) IND/IDE Assistance Program (MIAP) office for reporting of any and all IND safety reports to the FDA as per the requirements outlined in 21 CFR312.32. This includes reporting of all Serious Adverse Events (SAEs) that are both unexpected and related to the drug as soon as possible, but in no case later than 15 calendar days after the sponsor determines that the information qualifies for reporting. If the unexpected and related SAE is either fatal or life-threatening, then the SAE must be reported as soon as possible but in no case later than 7 calendar days after the sponsor's initial receipt of the information. A summary of all non-expedited safety reports will be submitted in the annual report.

For fatal or life-threatening SAEs where important or relevant information is missing, active follow-up is undertaken immediately. Investigators or other site personnel will inform the Sponsor designee of any follow-up information on a previously reported SAE immediately but no later than 24 hours of the Investigator's awareness of the event.

